5. TEST ARTICLE ALLOCATION AND MASKING

5.1. Test Article Allocation

The study lenses will be worn in a bilateral and random fashion using a 2×2 crossover design. A computer-generated randomization scheme will be used to randomly assign subjects, in blocks of 2, to one of the two possible lens wear sequences: Test/Control or Control/Test. The random scheme will be generated using the PROC PLAN procedure from Statistical Analysis System (SAS) Software Version 9.4 or higher (SAS Institute, Cary, NC).

The study site must follow the randomization scheme provided and complete enrollment per the randomization list and not pre-select or assign subjects. The randomized assignment of subjects will be performed at the first visit prior to the first fitting. The following must have occurred prior to randomization:

- Informed consent has been obtained
- Subject meets all the inclusion / exclusion criteria
- Subject history and baseline information has been collected.

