4. STUDY DESIGN AND RATIONALE

4.1. Description of Study Design

This is a 6-visit, subject-masked, multi-site, 2×2 crossover dispensing trial. A total of approximately 85 subjects will be enrolled with a target of 70 subjects to complete the study.

The study begins with an initial visit (Visit 1). If a subject is found to meet all eligibility criteria, they will be randomized to one of two lens wear sequences (Test/Control or Control/Test) in a bilateral fashion.

If the subject is dispensed study lenses at the initial visit, five additional visits will be conducted. The first follow-up visit (Visit 2) will occur 3 ± 1 days after the initial visit. At visit 2, subjects will undergo lens optimization if necessary. Subjects will wear the study lenses for 7 ± 1 days and then will return for their second follow-up at Visit 3. After Visit 3, subjects will undergo a washout period of 7 ± 3 days, where subjects will wear their habitual contact lenses or spectacles. After the washout period subjects will return for Visit 4, where they will be dispensed their second study lens per the randomization schedule. Subjects will return for their first follow-up visit (Visit 5) 3 ± 1 days after Visit 4, for lens optimization. Subjects will return for their second follow-up visit and their final evaluation 7 ± 1 days after Visit 5.

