5.2. Masking

This is a single-masked study with the subjects being masked. The term partial masking is being used as subjects will not be told any information regarding the optical designs of the lenses beyond that they are intended to correct for their refractive error and presbyopia, however there are slight differences in the tint of the lenses which is impossible to mask from the subject.

Under normal circumstances, the mask should not be broken until all subjects have completed the study and the database is finalized. Otherwise, the mask should be broken only if specific emergency treatment/course of action would be dictated by knowing the treatment status of the subject. In such cases, the Investigator may, in an emergency, contact the medical monitor. In the event the mask is broken, the Sponsor must be informed as soon as possible. The date, time, and reason for the unmasking must be documented in the subject record. The Investigator is also advised not to reveal the study treatment assignment to the clinical site or Sponsor personnel.

Subjects who have had their treatment assignment unmasked are expected to return for all remaining scheduled evaluations. Subjects who are discontinued may be replaced.

Clinical Study Protocol

Johnson & Johnson Vision Care, Inc.

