5.3. Procedures for Maintaining and Breaking the Masking

The test articles mask shall not be broken unless information concerning the lens type is necessary for the urgent medical treatment of a subject. The Sponsor must be notified before the mask is broken.

When dispensing test articles, the following steps should be followed to maintain randomization codes:

1. Investigator or designee (documented on the Delegation Log) will consult the lens fitting schedule/randomization scheme to obtain the test article assignment for that subject prior to dispensing.
2. Investigator or designee will record the subject's number on the appropriate line of the randomization scheme if applicable
3. Investigator or designee will pull the appropriate test articles from the study supply. All test articles that are opened, whether dispensed (placed/fit on eye or dispensed outside the clinical site) or not, must be recorded on the Test Article Accountability Log in the "Dispensed" section.

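### Fixed blocks of 2 and a scheme read by unmasked site staff leave sequence assignment predictable; any bias in the lens comparison is conditional and modest, and concealment is cheap

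*Combined protocol and SAP*

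**What the plan says.** Section 4.1 states that eligible subjects enter a 2×2 crossover: "they will be randomized to one of two lens wear sequences (Test/Control or Control/Test) in a bilateral fashion". Section 5.1 has a SAS-generated scheme assign them "in blocks of 2, to one of the two possible lens wear sequences". The block size is fixed.

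On masking, Section 5.2 says: "This is a single-masked study with the subjects being masked". Under Section 5.3 the investigator or a delegated staff member "will consult the lens fitting schedule/randomization scheme to obtain the test article assignment for that subject prior to dispensing". That person then enters, where applicable, the subject's "number on the appropriate line of the randomization scheme", and pulls the lenses from stock.

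The plan has two safeguards. Section 5.1 tells the site to "complete enrollment per the randomization list and not pre-select or assign subjects". On timing it says: "The randomized assignment of subjects will be performed at the first visit prior to the first fitting". Consent, eligibility and baseline data must come first, and the visit tables agree: eligibility is step 1.20 and randomization is step 1.21.

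The plan describes no sealed envelopes, no central or electronic release, no independent list holder and no varying block size. It gives neither the number of sites nor whether blocks run within site. Section 5.2 also advises the investigator not to disclose the assignment to site personnel, which sits awkwardly with Section 5.3, where a site designee looks it up.

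**The concern.** Randomization protects a comparison only if whoever enrols the next subject cannot tell what that subject will receive. Here the staff who book, screen and enrol know each assignment once it is made. They also know from the protocol that every consecutive pair contains one of each order. If they can see the scheme itself, they may know more than that.

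Staff could then decide, deliberately or not, whom to bring in for which order. In a parallel-group trial that would threaten the treatment contrast directly. In this crossover every subject is meant to wear both lenses, so the risk is narrower: the two sequence groups could differ in how scores drift from period 1 to period 2. In a 2×2 design such a difference cannot be told apart from a lens effect.

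**Working it through.** The plan gives no figure for predictability or balance, so there is nothing of its own to reproduce.

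**Inputs from the documents.** Blocks of 2 and two sequences (5.1); 70 completers (4.1); margin 5 CLUE points (2.3); SD 19.58 and ICC 0.3, 0.6, 0.8 (14.2, Table 5); two-sided 95% interval, so one-sided 0.025 (14.5). **Assumptions.** Blocks run within site, 1 to 12 sites, and the steering scenarios in steps 3 and 4.

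**1. Predictability when only past assignments are known.** For each position in a block, take the chance that the next assignment is forced and the chance that the best guess is right, then average over positions.

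- Blocks of 2: certain (0 + 1)/2 = 50%; guessed (0.5 + 1)/2 = 75%.
- Blocks of 4: certain (0 + 0 + 1/3 + 1)/4 = 33.3%; guessed (1/2 + 2/3 + 2/3 + 1)/4 = 70.8%.
- Blocks of 6: certain (0 + 0 + 0 + 0.1 + 0.4 + 1)/6 = 25%; guessed (0.5 + 0.6 + 0.6 + 0.7 + 0.7 + 1)/6 = 68.3%.

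If the full list can be read, the figure is 100% for every block size.

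**2. What steering can do to the lens difference.** Let τ be the true Test minus Control difference. Let π be the mean change from period 1 to period 2 that is unrelated to the lens. Subjects on Test/Control estimate τ − π(TC), and those on Control/Test estimate τ + π(CT). The average is τ + [π(CT) − π(TC)]/2.

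A common period change cancels. A difference between groups in general scoring level never enters, because each subject is compared with himself or herself. Only a difference in period change between the groups biases the result. The model in 14.5 cannot remove it: sequence, period and lens already use up the four cell means.

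**3. Size under hypothetical steering.** Suppose that in every pair the subject higher on some trait goes to one order. The expected gap between sequence groups is 2/√π = 1.128 trait SDs (here π is 3.1416). If the trait shifts the period change by g points per SD, the absolute bias is 1.128g/2 = 0.564g.

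| g (points per SD) | Full steering: formula (simulated) | Half-effective: formula (simulated) |
|---|---|---|
| 0 | 0 (0.00) | 0 (0.04) |
| 2 | 1.13 (1.15) | 0.56 (0.53) |
| 4 | 2.26 (2.28) | 1.13 (1.09) |

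The 0.04 is simulation noise. At g = 0 with ICC 0.6, full steering separates the groups by about 17 CLUE points in general level (19.58 × √0.6 × 1.128 = 17.1) and still leaves the lens difference unbiased.

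**4. A second illustration.** Suppose 20 percentage points more subjects in one order gain an extra 10 points in period 2. The bias is 0.5 × 0.20 × 10 = 1.0 point, or 20% of the margin. With SE = 19.58 × √(2(1 − ICC)/70), the SEs are 2.77, 2.09 and 1.48. If the bias favoured Test, the one-sided error 1 − Φ(1.96 − 1/SE) would be 5.5%, 6.9% and 10.0% instead of 2.5%.

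**5. What blocks of 2 buy.** Relative efficiency is 4p(1 − p), where p is the share in one sequence. With 70 subjects and 1 to 12 sites, simulated means were 0.9988–1.0000 for blocks of 2, 0.9980–0.9997 for 4 and 0.9974–0.9997 for 6. The largest mean loss is 0.9988 − 0.9974 = 0.0014, equivalent to 0.0014 × 70 = 0.1 subject. In the least balanced 5% of runs at 12 sites, efficiency was at or below 0.9967 for blocks of 2 and 0.9869 for blocks of 6, a difference of about 1%.

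**The case against.** Several points on the other side are fair.

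- **The readable list is an inference.** Section 5.3 speaks of looking up the assignment for the subject at hand, and of entering the number only where applicable. Step 1.21 says only to record a randomization ID. Section 5.1's reference to a scheme provided to the site makes a site-held list likely, but nothing says that future lines are visible. This stands.
- **The 50% and 75% need blocks within site, or staff who see consecutive assignments.** This also stands.
- **Block size is the weaker lever.** With a visible list it is irrelevant. Without one, moving from 2 to 4 or 6 lowers correct guesses only from 75% to 71% or 68%. This stands, and is why concealed release has to be part of the fix.
- **The plan already forbids pre-selection and places randomization after eligibility.** These rules reduce the risk. They are instructions, not concealment: a person who knows the next assignment can still decide whom to book or enrol next.
- **There is no evident motive.** Every subject is due to wear both lenses, and nothing in the documents suggests steering. This keeps the point minor.

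A reader might also infer that order decides who is lost, because a subject who fails dispensing on the first lens is discontinued. That does not support this point. Such losses occur under perfect concealment too. The same dispensing criteria apply at Visit 1 (step 1.32) and Visit 4 (step 4.17), and the per-protocol set in 14.3 requires all visits. A subject who fails dispensing on either lens is therefore excluded in either order.

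**Conclusion.** The point holds as a low-severity design weakness. The documents establish fixed blocks of 2 disclosed in the protocol, masking of subjects only, site staff who consult the scheme, and no described concealment. The predictability figures depend on blocks running within site; knowledge of every assignment depends on the list being visible.

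The effect on the primary comparison is conditional. It is zero without steering, and zero if steering follows general scoring level. If the steering trait also predicts change between periods, hypothetical inputs give about 1–2 CLUE points (2.3 in the most extreme case tried) against a margin of 5, direction unknown.

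A reader might infer that the non-inferiority test really runs at a 5.5–10% error rate, or that sites will choose the order. The documents support neither. Those rates follow only from an assumed 1-point bias in favour of Test, and no input to that bias comes from the trial. The case for change is that blocks of 2 bring almost no benefit over 4 or 6, and the remedy costs little.

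**What to change.** - **Section 5.1:** use randomly mixed blocks of 4 and 6, state that they run within site, and keep the sizes out of the site-facing protocol. Hold them in a document the sites do not see.
- **Section 5.3:** replace the readable scheme with release of one assignment at a time, after eligibility is recorded at step 1.20. Use sequentially numbered sealed envelopes, or the EDC system if it can be configured for this; Section 15.1 describes it for data capture only.
- **Section 5.2:** reconcile the advice on not disclosing assignments to site personnel with the staff roles in 5.3.

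The cost is a changed SAS call, a set of envelopes or an EDC setting, and one small step at Visit 1. Sequence balance within small sites becomes slightly looser, at a mean efficiency loss of about 0.15% at most under the 1 to 12 sites assumed. Sample size and analysis model do not change.

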5.2. Masking

This is a single-masked study with the subjects being masked. The term partial masking is being used as subjects will not be told any information regarding the optical designs of the lenses beyond that they are intended to correct for their refractive error and presbyopia, however there are slight differences in the tint of the lenses which is impossible to mask from the subject.

Under normal circumstances, the mask should not be broken until all subjects have completed the study and the database is finalized. Otherwise, the mask should be broken only if specific emergency treatment/course of action would be dictated by knowing the treatment status of the subject. In such cases, the Investigator may, in an emergency, contact the medical monitor. In the event the mask is broken, the Sponsor must be informed as soon as possible. The date, time, and reason for the unmasking must be documented in the subject record. The Investigator is also advised not to reveal the study treatment assignment to the clinical site or Sponsor personnel.

Subjects who have had their treatment assignment unmasked are expected to return for all remaining scheduled evaluations. Subjects who are discontinued may be replaced.

Clinical Study Protocol

Johnson & Johnson Vision Care, Inc.

5.3. Procedures for Maintaining and Breaking the Masking

The test articles mask shall not be broken unless information concerning the lens type is necessary for the urgent medical treatment of a subject. The Sponsor must be notified before the mask is broken.

When dispensing test articles, the following steps should be followed to maintain randomization codes:

1. Investigator or designee (documented on the Delegation Log) will consult the lens fitting schedule/randomization scheme to obtain the test article assignment for that subject prior to dispensing.
2. Investigator or designee will record the subject's number on the appropriate line of the randomization scheme if applicable
3. Investigator or designee will pull the appropriate test articles from the study supply. All test articles that are opened, whether dispensed (placed/fit on eye or dispensed outside the clinical site) or not, must be recorded on the Test Article Accountability Log in the "Dispensed" section.

6. STUDY INTERVENTION

6.1. Identity of Test Articles

The following contact lenses will be used in this study:

Table 1: Test Articles

	Test	Control
Name	JJVC Investigational Multifocal Contact Lens	Dailies Total 1® Multifocal Contact Lens

Clinical Study Protocol
Johnson & Johnson Vision Care, Inc.

Manufacturer	Johnson & Johnson® Vision Care, Inc.	Alcon
[REDACTED]	[REDACTED]	Over-labeled (marketed product)
Lens Material	Senofilcon A (C3)	Delefilcon A
Nominal Base Curve	8.35 mm	8.5 mm
Nominal Diameter	14.3 mm	14.1 mm
Nominal Distance Powers (D)	-1.00 D to -4.00 D in 0.25 D steps	-1.00 D to -4.00 D in 0.25 D steps
Nominal Cylinder Powers (D) and Axes	None	None
Nominal ADD Powers (D)	LOW, MID, HI	LO, MED, HI
Water Content	38%	33%
Center [contact] D	0.07 [contact] D	0.09 [contact] D
Oxygen Permeability (Dk)	103	[contact] D
Wear Schedule in Current Study	Daily Wear	Daily Wear
Replacement Frequency	Daily	Daily
Packaging Form (vial, blister, etc.)	Blister	Blister

6.2. Ancillary Supplies/Products

The following solutions will be used in this study:

Clinical Study Protocol

Johnson & Johnson Vision Care, Inc.

Table 2: Ancillary Supplies

Single-Use Preservative-Free Rewetting Solutions (any one of these three rewetting solutions options may be supplied)			
Solution Name/Description	Eye-Cept® Rewetting Drops	ScleralFil® Preservative Free Saline Solution	LaciPure Saline Solution
Manufacturer	Optics Laboratory	B&L	Menicon
Preservative	Non-Preserved	Non-preserved	Non-preserved

6.3. Administration of Test Articles

Test articles will be dispensed to subjects meeting all eligibility requirements, including any dispensing requirements set forth in this clinical protocol. Subjects will be dispensed an adequate supply of test articles to complete the study. Lost or damaged test articles may be replaced at the discretion of the Investigator and/or the Sponsor.

6.4. Packaging and Labeling

The test articles will be packaged in blisters, as the primary packaging. The test article will be over-labeled to mask the subject to the identity of the lens. The test articles will be in investigational cartons sealed with a tamper evident seal, commercial cartons, or in plastic bags as the secondary packaging form. The sample study label is shown below:

6.5. Storage Conditions

Test articles will be maintained at ambient temperatures at the clinical site. Test articles must be kept under secure conditions.

Clinical Study Protocol

Johnson & Johnson Vision Care, Inc.

6.6. Collection and Storage of Samples

When possible, any lens or test article associated with an Adverse Event and/or a Product Quality Complaint must be retained and stored in a glass vial with moderate solution pending directions from the sponsor for potential return to JJVC.

6.7. Accountability of Test Articles

JJVC will provide the Investigator with sufficient quantities of study articles and supplies to complete the investigation. The Investigator is asked to retain all lens shipment documentation for the test article accountability records.

Test articles must be kept in a locked storage cabinet, accessible only to those assigned by the Investigator for dispensing. The Investigator may delegate this activity to authorized study site personnel listed on the Site Delegation Log. All test articles must be accounted. This includes:

1. What was dispensed for the subject for trial fitting, to wear out of the office, or issued for the subject to replace appropriately between visits.
2. What was returned to the Investigator unused, including expired or malfunctioning product.
3. The number and reason for unplanned replacements.

The Investigator will collect all unused test articles from the subjects at the end of the subject's participation. Subject returned unused test articles must be separated from the clinical study inventory of un-dispensed test articles and must be labeled with the subject number and date of return. Following final reconciliation of test articles by the monitor, the Investigator or monitor will return all unused test articles to JJVC.

If there is a discrepancy between the shipment documents and the contents, contact the study monitor immediately.

Clinical Study Protocol

Johnson & Johnson Vision Care, Inc.

7. STUDY EVALUATIONS

7.1. Time and Event Schedule

Table 3: Time and Events

Visit Information	Visit 1 Screening, Baseline, Treatment 1	Visit 2 Treatment 1 Follow-up 1 Optimization	Visit 3 Treatment 1 Follow-up 2	Visit 4 Baseline Treatment 2	Visit 5 Treatment 2 Follow-up 1 Optimization	Visit 6 Treatment 2 Follow-up 2
Time Point	Day 0	Day 3±1 from V1	Day 7±1 from V2 Complete 7 ± 3 days washout before V4 (Day 0 for wash-out)	Day 7±3 from V3 Day 0	Day 3±1 from V4	Day 7±1 from V5
Estimated Visit Duration	2.5 hours	1.0 hour	1.5 hour	1.5 hour	1.0 hour	1.5 hour
Statement of Informed Consent	x					
Demographics	x					
Medical History/Concomitant Medications	x					
Adverse Events and Concomitant Medications Review		x	x	x	x	x
Compliance		x	x	x	x	x

Clinical Study Protocol

Johnson & Johnson Vision Care, Inc.

Visit Information	Visit 1 Screening, Baseline, Treatment 1	Visit 2 Treatment 1 Follow-up 1 Optimization	Visit 3 Treatment 1 Follow-up 2	Visit 4 Baseline Treatment 2	Visit 5 Treatment 2 Follow-up 1 Optimization	Visit 6 Treatment 2 Follow-up 2
Time Point	Day 0	Day 3±1 from V1	Day 7±1 from V2 Complete 7±3 days washout before V4 (Day 0 for wash-out)	Day 7±3 from V3 Day 0	Day 3±1 from V4	Day 7±1 from V5
Estimated Visit Duration	2.5 hours	1.0 hour	1.5 hour	1.5 hour	1.0 hour	1.5 hour
Habitual Contact Lens Information	x					
Contact Lens History	x					
Wear Time and Comfortable Wear Time with Habitual lenses	x					
Wear Time and Comfortable Wear Time with Study lenses	x		x	x	x	x
Screening Inclusion/Exclusion Criteria	x					
Subject Reported Ocular Symptoms	x	x	x	x	x	x
Baseline PRO (CLUE and MRD) Questionnaire	x					
CLDEQ-8 Questionnaire	x		x			x
Distance and Near Entrance Visual Acuity	x	x	x	x	x	x

Clinical Study Protocol

Johnson & Johnson Vision Care, Inc.

Visit Information	Visit 1 Screening, Baseline, Treatment 1	Visit 2 Treatment 1 Follow-up 1 Optimization	Visit 3 Treatment 1 Follow-up 2	Visit 4 Baseline Treatment 2	Visit 5 Treatment 2 Follow-up 1 Optimization	Visit 6 Treatment 2 Follow-up 2
Time Point	Day 0	Day 3±1 from V1	Day 7±1 from V2 Complete 7±3 days washout before V4 (Day 0 for wash-out)	Day 7±3 from V3 Day 0	Day 3±1 from V4	Day 7±1 from V5
Estimated Visit Duration	2.5 hours	1.0 hour	1.5 hour	1.5 hour	1.0 hour	1.5 hour
Lens Removal	x	x	x	x	x	x
Keratometry	x					
Subjective Refraction and Distance Visual Acuity	x					
Near ADD Determination	x					
Ocular Dominance	x					
ADD Refinement	x					
Near Visual Acuity	x					
Biomicroscopy	x	x	x	x	x	x
Baseline Inclusion/Exclusion Criteria	x					
Continuance				x	x	
Lens Selection	x	x (if modified)		x	x (if modified)	
Lens Insertion	x	x		x	x	
10 Minute Settling	x	x		x	x	
Visual Satisfaction / Subjective Acceptance	x	x	x	x	x	x

Clinical Study Protocol

Johnson & Johnson Vision Care, Inc.

Visit Information	Visit 1 Screening, Baseline, Treatment 1	Visit 2 Treatment 1 Follow-up 1 Optimization	Visit 3 Treatment 1 Follow-up 2	Visit 4 Baseline Treatment 2	Visit 5 Treatment 2 Follow-up 1 Optimization	Visit 6 Treatment 2 Follow-up 2
Time Point	Day 0	Day 3±1 from V1	Day 7±1 from V2 Complete 7±3 days washout before V4 (Day 0 for wash-out)	Day 7±3 from V3 Day 0	Day 3±1 from V4	Day 7±1 from V5
Estimated Visit Duration	2.5 hours	1.0 hour	1.0 hour	1.5 hour	1.5 hour	1.0 hour
Study Lens Distance and Near Visual Acuity	x	x	x	x	x	x
Distance Over Refraction and Visual Acuity	x	x		x	x	x
Subjective Lens Fit Assessment	x	x	x	x	x	x
Lens Deposits			x			x
Lens Wettability			x			x
Binocular Over Refraction			x			x
C-Quant Straylight Meter Testing			x			x
Corneal Topography and Wavefront measurement				x		x
Compliance		x	x		x	x
Follow-up PRO (CLUE / MRD) Questionnaire		x	x		x	x
Visual Performance			x			x
Modifications	x	x		x	x	x

Clinical Study Protocol

Johnson & Johnson Vision Care, Inc.

Visit Information	Visit 1 Screening, Baseline, Treatment 1	Visit 2 Treatment 1 Follow-up 1 Optimization	Visit 3 Treatment 1 Follow-up 2	Visit 4 Baseline Treatment 2	Visit 5 Treatment 2 Follow-up 1 Optimization	Visit 6 Treatment 2 Follow-up 2
Time Point	Day 0	Day 3±1 from V1	Day 7±1 from V2 Complete 7±3 days washout before V4 (Day 0 for wash-out)	Day 7±3 from V3 Day 0	Day 3±1 from V4	Day 7±1 from V5
Estimated Visit Duration	2.5 hours	1.0 hour	1.5 hour	1.5 hour	1.0 hour	1.5 hour
Post-Fit PRO (MRD) Questionnaire	x	x		x	x	
Distance and Near Exit Visual Acuity	x	x	x	x	x	
Dispensing Criteria	x	x		x	x	
Instructions	x	x	x	x	x	
Schedule Follow-up	x	x	x	x	x	
Final Evaluation					x	

Clinical Study Protocol
Johnson & Johnson Vision Care, Inc.

